4.4.4 Storage

Investigational product must be stored in the original outer package and must not be thawed. The manufacturer's instructions for shipment and storage will be followed at all times. It is the responsibility of the investigator to maintain daily temperature logs for the freezer, at a minimum, daily Monday through Friday. The investigator will be provided with temperature monitors that record minimum/maximum temperatures, unless temperature monitors are already in place.

4.4.5 Treatment Compliance

Investigational product is administered by study site personnel, who will monitor compliance.

4.4.6 Accountability

The investigator's or site's designated investigational product manager is required to maintain accurate investigational product accountability records. Upon completion of the study, copies of investigational product accountability records will be returned to MedImmune. All unused investigational product will be returned to a MedImmune-authorized depot or disposed of upon authorization by MedImmune.

4.5 Treatment Assignment and Blinding

4.5.1 Methods for Assigning Treatment Groups

An IWRS will be used for randomization to a treatment group and assignment of blinded investigational product sprayer numbers. A subject is considered randomized into the study when the investigator notifies the IWRS that the subject meets eligibility criteria and the IWRS provides the assignment of blinded investigational product sprayer numbers to the subject.

Subjects will be randomized at a 4:1 ratio to receive either bivalent influenza vaccine or placebo. The randomization will be stratified by site.

Investigational product (bivalent influenza vaccine or placebo) must be administered the same day the investigational product is assigned. If there is a delay in the administration of investigational product such that it will not be administered within the specified timeframe, the study monitor must be notified immediately.

4.5.2 Methods for Ensuring Blinding

This is a double-blind study in which bivalent influenza vaccine and placebo are identically labeled and indistinguishable in appearance. As such, neither the subject/legal representative nor any of the investigator or sponsor staff who are involved in the treatment or clinical evaluation of the subjects will be aware of the treatment received (ICH E9; see Section 4.5.3.2 for unblinding related to interim planned analysis). In the event that treatment allocation for a subject becomes known to the investigator or other study staff involved in the management of study subjects, the sponsor must be notified *immediately*.

4.5.3 Methods for Unblinding

4.5.3.1 Unblinding in the Event of a Medical Emergency

In the event of a medical emergency, the investigator may unblind an individual subject's investigational product allocation. Prior to unblinding the investigational product allocation for an individual subject, the investigator must first attempt to contact the medical monitor to discuss the medical emergency and the reason for wanting to unblind. Instructions for unblinding an individual subject's investigational product allocation are contained in the IWRS manual. In general, unblinding should only occur if management of the medical emergency would be different based on the subject having received investigational product. In the majority of cases, the management of a medical emergency would be the same whether or not investigational product was received by the subject. If this was the case, the investigational product allocation should not be unblinded.

MedImmune retains the right to unblind the treatment allocation for SAEs that are unexpected and are suspected to be causally related to an investigational product and that potentially require expedited reporting to regulatory authorities.

4.5.3.2 Unblinding for Interim Analysis

An interim analysis is planned for this study as described in Section 4.7.4. To ensure the blinding of each subject's treatment assignment throughout the study, the Day 15 unblinded analyses will be performed by defined MedImmune personnel, including the medical monitor, the clinical program manager, Patient Safety staff team members, Regulatory (Clinical) staff team members, a Medical Writing staff team member, a Biostatistics staff team member, Clinical Statistical Analysis System Programming staff team members, and Data Management (including data management vendor's non-MedImmune personnel) staff team members. Study site personnel and contract research organization personnel directly associated with the conduct of this study and the subjects will remain blinded to the treatment assignment for individual subjects until the completion of the study.

4.6 **Restrictions During the Study and Concomitant Treatment(s)**

The Investigator must be informed as soon as possible about any medication taken from the time of screening until the end of the clinical phase of the study (final study visit). Any concomitant medication(s), including herbal preparations, taken during the study will be recorded in the electronic case report form (eCRF).

4.6.1 **Permitted Concomitant Medications**

Investigators may prescribe concomitant medications or treatments deemed necessary to provide adequate supportive care except for those medications identified as "excluded" as listed in Section 4.6.2. Specifically, subjects should receive full supportive care during the study, including transfusions of blood and blood products, and treatment with antibiotics, anti-emetics, anti-diarrheals, and analgesics, and other care as deemed appropriate, and in accordance with their institutional guidelines.

4.6.2 Prohibited Concomitant Medications

Other than the medications described above, use of concomitant medications including overthe-counter medications, herbal supplements, vitamins, etc, from Day 1-15 is discouraged. Subjects must be instructed not to take any medications, including over-the-counter products, without first consulting with the investigator.

Use of antipyretic or analgesic medications for all symptoms other than temperatures $\geq 101^{\circ}$ F oral (or equivalent) is discouraged from Day 1-15. All medications taken during the 14-day post vaccination follow-up period, the indications, the start and stop dates of the medications, and the route of administration will be recorded from the time of informed consent through Day 15.

The following medications are exclusionary. The sponsor must be notified if a subject receives any of these during the study.

- 1 Any vaccine or investigational agent from 30 days prior to randomization through 30 days post investigational product administration
- 2 Any intranasal medication from 14 days prior to through 14 days post investigational product administration
- 3 Receipt of influenza antiviral therapy or antiviral agents within 48 hours prior to investigational product administration or expected receipt of influenza antiviral therapy or antiviral agents through 14 days after receipt of investigational product

4.7 Statistical Evaluation

4.7.1 General Considerations

Data will be provided in data listings sorted by treatment group and subject identification number. Tabular summaries will be presented by treatment group. Categorical data will be summarized by the number and percentage of subjects in each category. Continuous variables will be summarized by descriptive statistics, including mean, standard deviation, median, minimum, and maximum. Confidence intervals (CIs) will be two-sided, unless otherwise stated.

The intent-to-treat (ITT) population is defined as all subjects that are randomized and treated with investigational product. All analyses will be performed on the ITT population unless otherwise specified. Missing will be treated as missing and no data will be imputed.

4.7.2 Sample Size and Power Calculations

It is expected that almost all subjects will provide information on safety and tolerability. Table 4 summarizes the solicited event rates following FluMist and placebo vaccination in healthy adults 18 through 64 years of age in Study AV009.

Number of Subjects	FluMist ^a	Placebo ^a	Difference in Proportions	95% CI ^b
Randomized	3,041	1,520		
Who returned diary cards	2,985	1,490		
Who experienced solicited events	n (%)	n (%)		
Fever				
Oral temperature > 100.0°F	40 (1.34)	20 (1.34)	-0.00	(-0.01, 0.01)
Oral temperature $\geq 101.0^{\circ}$ F	17 (0.57)	9 (0.60)	-0.00	(-0.01, 0.00)

Table 4Summary of Solicited Events (Days 0 Through 7) in Study AV009

Number of Subjects	FluMist ^a	Placebo ^a	Difference in Proportions	95% CI ^b
Oral temperature > 102.0°F	2 (0.07)	2 (0.13)	-0.00	(-0.01, 0.00)
Oral temperature > 103.0°F	0	0	0.00	(-0.00, 0.00)
Runny nose	1,323 (44.32)	397 (26.64)	0.18	(0.15, 0.21)
Sore throat	793 (26.57)	243 (16.31)	0.10	(0.08, 0.13)
Cough	407 (13.64)	152 (10.20)	0.03	(0.01, 0.06)
Headache	1,172 (39.26)	555 (37.25)	0.02	(-0.01, 0.05)
Muscle aches	481 (16.11)	216 (14.50)	0.02	(-0.00, 0.04)
Chills	247 (8.28)	91 (6.11)	0.02	(0.00, 0.04)
Tired/weak	733 (24.56)	306 (20.54)	0.04	(0.01, 0.07)
Any solicited event	2,117 (70.92)	919 (61.68)	0.09	(0.06, 0.12)

Table 4	Summary of Solicited Events	(Days 0 Through 7) in Study AV009
			,

CI = confidence interval

^a Subjects counted if they experienced an event at least once within 7 days following vaccination.

^b Confidence intervals for the difference in proportions are based on an exact method.

Power to show a similar fever rate with 300 evaluable subjects (240 bivalent vaccine and 60 placebo recipients) for varying true fever rates ranging from 0.5% to 2.0% in placebo recipients is presented in Table 5. Accordingly, the currently proposed study will provide at least 98% power to rule out a rate increase of 5 percentage points assuming the true difference between the treatment groups is zero and the true fever rate is $\leq 1\%$. Power is lower if the true difference is different from zero. For example, if the true fever rates are 2% and 1% in vaccine and placebo recipients, respectively, the power will be 77%.

True Fever Rate			
Vaccine	Placebo	Exact Power ^a	Exact Type I Error Rate
0.5%	0.5%	99.9%	2.2%
1.0%	1.0%	98.0%	2.3%
1.5%	1.5%	92.6%	2.3%
2.0%	2.0%	85.0%	2.3%
2.0%	1.0%	77.0%	2.3%
3.0%	1.0%	43.9%	2.3%

Note: Similar fever rates mean the ability to rule out a 5 percentage point increase in vaccine recipients. Total N includes 240 vaccine recipients and 60 placebo recipients.

^a Power was computed using the method proposed by Chan and Zhang, 1999.

Power to show similar event rates for other solicited symptoms with 300 evaluable subjects (240 bivalent vaccine and 60 placebo recipients) for rates ranging from 6% to 37% in placebo recipients is presented in Table 6. Accordingly, the currently proposed study provides at least 87% power to rule out a 20 percentage point increase, assuming the true difference between the 2 treatment groups is zero. Power is lower if the true difference is greater than zero.

	True Event Rates		Rate Increase to be	
Solicited Events	Vaccine	Placebo	Ruled Out (PPT)	Power ^a
Runny nose	27%	27%	20	94%
	44%	27%	20	8%
	44%	27%	36	90%
Sore throat	16%	16%	15	92%
	27%	16%	15	13%
	27%	16%	27	91%
Cough	10%	10%	15	99%
	14%	10%	15	82%
	14%	10%	17	93%
Headache	37%	37%	20	87%
Muscle aches	15%	15%	15	93%
Chills	6%	6%	10	95%
Tired/weak	21%	21%	20	98%
	25%	21%	20	86%
	25%	21%	21	90%

Table 6Power For Secondary Endpoints

PPT = percentage point

Note: Total number includes 240 bivalent vaccine recipients and 60 placebo recipients.

^a Power was computed using the method proposed by (Chan, 1998) and Proc-Stat (Version 6.2) software.

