Each subject will receive one dose of investigational product on Day 1. Subjects will be followed through 180 days after receipt of investigational product.

TARGET SUBJECT POPULATION

The subjects in this study will be healthy adults 18 through 49 years of age (not yet reached their 50th birthday).

INVESTIGATIONAL PRODUCT, DOSAGE, AND MODE OF ADMINISTRATION

Eligible subjects will be randomly assigned in a 4:1 ratio to receive a single dose of either bivalent vaccine (240 subjects) or placebo (60 subjects) by intranasal spray on Day 1.

STATISTICAL ANALYSIS PLAN

General Considerations

Data will be provided in data listings sorted by treatment group and subject identification number. Tabular summaries will be presented by treatment group. Categorical data will be summarized by the number and percentage of subjects in each category. Continuous variables will be summarized by descriptive statistics,

including mean, standard deviation, median, minimum, and maximum. Confidence intervals (CIs) will be two-sided, unless otherwise stated.

The intent-to-treat (ITT) population is defined as all subjects that are randomized and treated with investigational product. All analyses will be performed on the ITT population unless otherwise specified.

Sample Size and Power Calculations

Based on the solicited event rates following FluMist[®] and placebo vaccination in healthy adults 18 to 64 years of age in Study AV009, the currently proposed study with 300 evaluable subjects (240 bivalent vaccine and 60 placebo recipients) will provide at least 98% power to rule out a rate increase of 5 percentage points assuming the true difference between the treatment groups is zero and the true fever rate is $\leq 1\%$. Power is lower if the true difference is different from zero. For example, if the true fever rates are 2% and 1% in vaccine and placebo recipients, respectively, the power will be 77%. For other solicited symptoms with 300 evaluable subjects (240 bivalent vaccine and 60 placebo recipients), the currently proposed study provides at least 87% power to rule out a 20 percentage point increase, assuming the true difference between the 2 treatment groups is zero. Power is lower if the true difference is greater than zero.

Assessment of Endpoints

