4 MATERIALS AND METHODS

4.1 Subjects

4.1.1 Number of Subjects

This study will enroll approximately 300 healthy adults 18 through 49 years of age (not yet reached their 50th birthday). Eligible subjects will be randomly assigned in a 4:1 fashion to receive a single dose of bivalent vaccine or placebo by intranasal spray.

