4.1.4 Subject Enrollment and Randomization

Study participation begins (ie, a subject is "enrolled") once written informed consent is obtained. Once informed consent is obtained, a subject identification (SID) number will be assigned by a central system (eg, an interactive web response system, IWRS), and the screening evaluations may begin to assess study eligibility (inclusion/exclusion) criteria. The SID number will be used to identify the subject during the screening process and throughout study participation, if applicable.

Subjects will be randomized at a 4:1 ratio to receive either a single dose of bivalent vaccine or placebo by intranasal spray. Randomization will be stratified by site.

A master log of all consented subjects will be maintained at the site and will document all screening failures (ie, subjects who are consented but do not meet study eligibility criteria and/or are not randomized), including the reason(s) for screening failure.

Subjects who fail to meet the inclusion/exclusion criteria (ie, screening failures) should not be randomized (if applicable) or receive investigational product.

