4.1.6 Replacement of Subjects

Subjects will not be replaced.

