4.7.3 Endpoints

4.7.3.1 Primary Endpoint

The primary endpoint of this study is fever (Days 1 through 8), defined as oral temperature $\geq 101^{\circ}$ F. Comparison of the rate of fever between the 2 treatment groups will be based on the upper limit of the two-sided 95% exact CIs for the rate increase (bivalent vaccine minus placebo) evaluated against the pre-specified equivalence criterion of 5 percentage points.

This corresponds to the null hypothesis of:

H0: Rate difference \geq 5 percentage points.

The alternative hypothesis is:

HA: Rate difference < 5 percentage points.

A two-sided 95% CI will be constructed using the exact method based on the score statistic proposed by (Chan and Zhang, 1999). This method computes the lower and upper confidence limits by inverting 2 separate one-sided tests of half the nominal Type I error rate. Its test statistic is based on the score statistic that is computed as the observed difference of the 2 binomial event rates minus the hypothesized value of the rate difference (observed rate difference) divided by the standard error of this difference under the alternative hypothesis. This test assures that the Type I error does not exceed the pre-specified level. Due to discreteness when the sample size is relatively small compared to the expected event rate, the associated Type I error rate could be quite conservative, that is, smaller than the pre-specified level.

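### The stated 98% and 77% power for fever apply only at exactly the 240/60 that will be randomized; losing any one subject lowers them to about 95% and 65–68%

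*Combined protocol and SAP*

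**What the plan says.** - **Power.** Section 4.7.2 says "the currently proposed study will provide at least 98% power to rule out a rate increase of 5 percentage points", assuming no true difference and a fever rate of at most 1%. It gives 77% for 2% versus 1%. The synopsis repeats both figures. Table 5 and its note are for 240 vaccine and 60 placebo recipients, described in the text as evaluable.
- **Numbers.** Section 4.1.1: "This study will enroll approximately 300 healthy adults". Section 3.1.2 assigns 240 to vaccine and 60 to placebo, so the planned and the evaluable numbers are the same.
- **Loss.** Section 4.1.6: "Subjects will not be replaced". Section 4.7.1 leaves missing data missing, without imputation. The only remark on completeness, at the start of Section 4.7.2, is an unquantified expectation that nearly everyone will supply safety data.
- **Test.** Section 4.7.3.1 takes the upper limit of a two-sided 95% exact interval for the rate difference, "evaluated against the pre-specified equivalence criterion of 5 percentage points". On the interval: "This method computes the lower and upper confidence limits by inverting 2 separate one-sided tests of half the nominal Type I error rate". The decision is therefore a one-sided exact test at 0.025.
- **Planning data.** Table 4 (Study AV009) has a row headed "Who returned diary cards": 2,985 of 3,041 FluMist and 1,490 of 1,520 placebo subjects. Fever of 101°F or more occurred in 0.57% and 0.60%.

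**The concern.** The power claim is about the study as proposed, but it is computed as if every randomized subject contributes a fever result. In most designs of this size one or two missing subjects would not matter. Here events are so rare that the decision turns on single fevers, and an exact test's rejection region changes in steps. If 240/60 lies at the edge of a step, the headline figure is the top of a sawtooth and does not describe the sample likely to be analysed.

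At stake is the accuracy of the stated power for the primary comparison, which Section 4.7.4 says will go to regulators to support commercial release. The 2% versus 1% case matters most: the true excess there is 1 point, well inside the 5-point margin, and the risk of missing the criterion is understated.

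**Working it through.** **Inputs.** Margin 5 points; one-sided level 0.025; exact unconditional test on the score statistic (Section 4.7.3.1); 240/60 and the true rates in Table 5 (Section 4.7.2).

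**Method.** For each pair of fever counts (x1, x0), compute

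Z = (x1/n1 − x0/n0 − 0.05) / SE,

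with SE taken from the maximum-likelihood rates constrained to differ by 0.05. The p-value is the probability of a Z at least as small, maximized over the placebo rate. The criterion is met when p ≤ 0.025. Power is the sum of the binomial probabilities of all passing pairs.

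**Step 1: reproduce Table 5 at 240/60.**

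| Vaccine/placebo rate | Table 5 | Recomputed |
|---|---|---|
| 0.5%/0.5% | 99.9% | 99.89% |
| 1%/1% | 98.0% | 97.98% |
| 1.5%/1.5% | 92.6% | 92.61% |
| 2%/2% | 85.0% | 85.02% |
| 2%/1% | 77.0% | 76.99% |
| 3%/1% | 43.9% | 43.88% |

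All six agree, so the method is the one the plan used.

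**Step 2: find the step.** Take 5 vaccine fevers and 0 placebo fevers:

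- 240/60: p = 0.0246, passes
- 239/60: p = 0.0254, fails
- 240/59: p = 0.0270, fails

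With no placebo fevers, the largest vaccine count that passes falls from 5 to 4.

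**Step 3: confirm that this one result explains the drop.** At 240/60 its probability is P(5 of 240) × P(0 of 60):

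- 1%/1%: 0.0600 × 0.5472 = 0.0328, or 3.3 points. The fall at 239/60 is 97.98 − 94.77 = 3.2 points.
- 2%/1%: 0.1766 × 0.5472 = 0.0966, or 9.7 points. The fall at 239/60 is 76.99 − 67.60 = 9.4 points.

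**Step 4: power at nearby evaluable numbers.**

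| Evaluable | 0.5%/0.5% | 1%/1% | 2%/1% | AV009 rates 0.57%/0.60% |
|---|---|---|---|---|
| 240/60 | 99.9% | 98.0% | 77.0% | 99.8% |
| 239/60 | 99.5% | 94.8% | 67.6% | 99.1% |
| 240/59 | 99.4% | 94.7% | 67.1% | 99.1% |
| 236/59 | 99.5% | 94.7% | 65.1% | 99.2% |
| 235/59 | 99.5% | 94.8% | 65.4% | 99.2% |

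Over every combination of 0–12 vaccine and 0–4 placebo losses with at least one loss, power is 94.5–95.3% at 1%/1% and 64.9–67.9% at 2%/1%. None keeps 98% or 77%.

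**Step 5: look above 240/60.** One extra placebo subject (240/61) also lowers power, to 94.8% and 67.6%. One extra vaccine subject (241/60) keeps 97.95% and 76.7%. A 241/59 split with nobody lost gives 94.6% and 66.8%. Power does not rise steadily with sample size here.

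**Step 6: how likely is full completeness?** The plan gives no figure, so this is an assumption, with subjects independent:

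- AV009 diary return, 2,985/3,041 = 98.2% and 1,490/1,520 = 98.0%: 0.9816^240 × 0.9803^60 ≈ 0.3%
- 99.5% per subject: 0.995^300 ≈ 22%
- 99.9% per subject: 0.999^300 ≈ 74%

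**The case against.** A reader might infer that Table 5 is wrong. It is not: every power figure reproduces, and both the synopsis and Section 4.7.2 state the evaluable numbers they assume.

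A reader might also infer that the trial is underpowered. The documents do not support that. They set no target power. At the AV009 fever rates power is about 99% with or without losses, and at 1%/1% it is still about 95%. The large fall occurs in an illustrative case that the plan itself introduces with a warning that power is lower.

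It is tempting to treat about 235/59 as the expected sample and 0.3% as the chance of full data. Both carry over AV009 diary return. Here staff collect symptoms by telephone every day or every other day to Day 15 (Section 4.2.3.2), the worksheet is only a memory aid (Section 4.2.2), telephone availability is an inclusion criterion, and the primary window ends at Day 8. Completeness could well be better. That weakens the forecast but not the result, because one loss is enough.

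Section 4.1.4 counts a subject as enrolled "once written informed consent is obtained", from which one might infer that far fewer than 300 will be dosed. Sections 3.1.2 and 4.1.4 answer this: 240 and 60 are the numbers randomly assigned, and screening failures are separate.

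Finally, this is discreteness and not ordinary loss of information, and enrolment is only approximately 300, so the realized counts could fall on a favourable step. This stands, and is a reason to report a range. Section 4.7.3.1 mentions discreteness only for Type I error, so it does not warn the reader about power.

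**Conclusion.** The point holds as a statement about the stated power; it should be fixed, but it does not threaten the trial. Table 5 is right at exactly 240/60 evaluable. The plan randomizes those numbers with no margin for loss, no replacement and no imputation, and itself expects slightly less than complete data. Once any subject is non-evaluable, the claim of at least 98% for rates up to 1% fails at the upper end of that range (about 95%), and 77% becomes about 65–68%. The chance of missing the criterion when the true rates are 2% and 1% goes from 23% to about a third.

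This assumes that a dosed subject without temperature data leaves the fever denominator. That follows from leaving missing data missing; keeping such a subject as having no fever would be imputation. The one-loss figures need no assumption about how many are lost. Only the 235/59 end of the range rests on AV009 diary return. The analysis, the margin and control of Type I error are unaffected.

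**What to change.** In the synopsis, Section 4.7.2 and Table 5:

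1. Keep the 240/60 figures, and say that 98% and 77% apply only when all 240 and 60 are evaluable for fever.
2. Add power over a realistic evaluable range, for example 239/60 down to 235/59, labelling the lower end as an assumption from AV009 diary return: about 99.5% at 0.5%/0.5%, about 95% at 1%/1%, and about 65–68% at 2%/1%.
3. Add a sentence that power under the exact test is a sawtooth in the arm sizes, so a change of one subject can move it by several points.

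The cost is wording, a few table rows and a slightly less favourable stated power. No subjects need be added. Enlarging the trial a little would not clearly recover the claims: 250/63, all evaluable, gives 97.7% and 74.8%.

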4.7.3.2 Secondary Endpoints

Secondary endpoints of the study include other reported solicited symptoms and AEs that occur within 7 days after vaccination (Days 1-8), and all solicited symptoms and AEs that occur within 14 days after vaccination (Days 1-15). Additional secondary endpoints include SAEs and NOCDs that occur within 28 days after vaccination (Days 1-29) and within 180 days after vaccination (Days 1 through 181).

Fever will be summarized according to the following thresholds:

- Oral $> 100^{\circ}$ F
- Oral $\geq 101^{\circ}$ F
- Oral $> 102^{\circ}F$
- Oral $> 103^{\circ}F$

A secondary analysis comparing rates of other solicited symptoms (Days 1-8) between the 2 treatment groups will be performed. Exact two-sided 95% CIs (Chan and Zhang, 1999) on the rate difference (bivalent vaccine minus placebo) will be constructed. There are no prespecified equivalence criteria for the secondary analyses.

The number of days of solicited symptoms and the proportion of subjects experiencing each event by study day will be presented without formal statistical comparison. The distribution of the number of days with each individual event will also be summarized without formal statistical comparison. The proportion of subjects using antipyretic and analgesic agents within 7 days after vaccination (Days 1-8) and 14 days after vaccination (Days 1-15) will be summarized by treatment group.

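### Table 6 and the 87% power floor for other solicited symptoms are up to about 2 points optimistic for the exact analysis that is planned

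*Combined protocol and SAP*

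**What the plan says.** Section 4.7.2 of the combined protocol and SAP gives power for the solicited symptoms other than fever in Table 6. The note under the table fixes the group sizes: "Note: Total number includes 240 bivalent vaccine recipients and 60 placebo recipients". Footnote a gives the source: "Power was computed using the method proposed by (Chan, 1998) and Proc-Stat (Version 6.2) software". The reference list shows the 1998 paper as one on exact tests of equivalence and efficacy.

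The text summarises the table by saying that "the currently proposed study provides at least 87% power to rule out a 20 percentage point increase" if the true difference is zero, and adds that power falls when the true difference is above zero. The synopsis repeats both statements. The figure comes from the row "Headache 37% 37% 20 87" (per cent).

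For the analysis itself, Section 4.7.3.2 states: "Exact two-sided 95% CIs (Chan and Zhang, 1999) on the rate difference (bivalent vaccine minus placebo) will be constructed". It also states: "There are no prespecified equivalence criteria for the secondary analyses".

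**The concern.** A power figure should describe the analysis that will be run. The footnote and the planned intervals both point to an exact method, so an exact calculation should return the Table 6 values. It does not: the exact figures are all lower. The summary sentence is worded as a floor, and the planned analysis falls below that floor in the row that sets it. What is at stake is the accuracy of a stated figure in the synopsis and in Section 4.7.2. No decision rule depends on it.

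**Working it through.** **Inputs.** Group sizes are 240 and 60 (note to Table 6). The one-sided level is 0.025, because Section 4.7.3.1 describes the Chan-Zhang interval as formed by "inverting 2 separate one-sided tests of half the nominal Type I error rate", and half of 5% is 2.5%. True rates, margins and printed powers are those of Table 6.

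**Statistic.** With x events in 240, y events in 60 and margin d:

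z = (x/240 − y/60 − d) / sqrt[ p1(1 − p1)/240 + p2(1 − p2)/60 ],

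where p1 and p2 are the maximum-likelihood rates under the restriction p1 − p2 = d. An increase of d is ruled out when z is small enough. Power is the sum of binomial probabilities, at the true rates, over all 241 × 61 outcomes that meet the criterion.

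**Two criteria.**

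- Asymptotic cut-off: z ≤ −1.96.
- Exact unconditional: the p-value is maximised over the unknown placebo rate and must be at most 0.025. At the Table 6 margins this puts the critical value between −2.035 (20 points) and −2.065 (10 points), which is stricter than −1.96.

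**Results (per cent).**

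| Symptom | Vaccine / placebo | Margin | Printed | 1.96 cut-off | Exact | Printed minus exact |
|---|---|---|---|---|---|---|
| Runny nose | 27 / 27 | 20 | 94 | 93.81 | 92.99 | 1.01 |
| | 44 / 27 | 20 | 8 | 7.63 | 6.52 | 1.48 |
| | 44 / 27 | 36 | 90 | 89.57 | 88.16 | 1.84 |
| Sore throat | 16 / 16 | 15 | 92 | 91.60 | 89.99 | 2.01 |
| | 27 / 16 | 15 | 13 | 12.95 | 11.46 | 1.54 |
| | 27 / 16 | 27 | 91 | 91.02 | 89.92 | 1.08 |
| Cough | 10 / 10 | 15 | 99 | 98.97 | 98.67 | 0.33 |
| | 14 / 10 | 15 | 82 | 82.37 | 79.96 | 2.04 |
| | 14 / 10 | 17 | 93 | 93.25 | 91.88 | 1.12 |
| Headache | 37 / 37 | 20 | 87 | 87.25 | 85.53 | 1.47 |
| Muscle aches | 15 / 15 | 15 | 93 | 93.14 | 91.79 | 1.21 |
| Chills | 6 / 6 | 10 | 95 | 94.95 | 93.90 | 1.10 |
| Tired/weak | 21 / 21 | 20 | 98 | 97.57 | 97.05 | 0.95 |
| | 25 / 21 | 20 | 86 | 85.90 | 84.29 | 1.71 |
| | 25 / 21 | 21 | 90 | 89.99 | 88.61 | 1.39 |

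The 1.96 cut-off reproduces all 15 printed values after rounding. The exact test reproduces one (cough, 10 / 10).

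**Other candidate methods.** The closed-form Farrington-Manning formula matches 2 of 15 rows and the unpooled Wald formula none. Four variants of the exact test match 5, 2, 1 and 1: critical value set at each row's own null rates, p-value at the restricted estimate, and Berger-Boos with gamma 0.001 and 0.000001.

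**The floor.** At zero difference and a 20-point margin, exact power falls as the common rate rises across the Table 6 range: 97.05% at 21%, 92.99% at 27% and 85.53% at 37%. Headache therefore sets the minimum under the exact test too, and the minimum is 85.5%.

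**Control.** The exact calculation returns all six Table 5 fever powers: 99.89, 97.98, 92.61, 85.02, 76.99 and 43.88, against the printed 99.9, 98.0, 92.6, 85.0, 77.0 and 43.9. This supports the exact calculation but does not separate the two criteria. The 1.96 cut-off gives 99.89, 97.98, 92.61, 85.04, 77.00 and 43.94 there, the same after rounding to one decimal. The evidence on the source of Table 6 comes from Table 6 alone.

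**The case against.** The strongest reply is that the gap is trivial. The headline moves by 1.5 points, 13 of 15 rows lie within 2 points of the printed figure, and the other two miss by 2.01 and 2.04 against values already rounded to whole per cents. With no equivalence criterion for the secondary analyses, nothing in the sample size, the intervals or the conclusions changes. All of that stands and sets the severity. It does not rescue a sentence that states a minimum which the planned analysis does not reach.

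Three stronger readings are tempting, and the documents do not support them.

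- A reader might infer that the plan hides a collapse in power at the rates of its source study, AV009, where runny nose occurred in "1,323 (44.32) 397 (26.64" (events and per cent, FluMist then placebo). The plan discloses this. The headline is conditional on zero difference, the next sentence says that power is lower otherwise, and Table 6 prints 8% for runny nose at 44% against 27% and 13% for sore throat at 27% against 16%. Nor is the fall general: at AV009 rates and a 20-point margin, exact power stays at about 99% or more for cough, muscle aches and chills.
- A reader might infer that the trial's secondary analysis will exceed its nominal error rate, because the 1.96 cut-off does not guarantee 2.5%. The planned intervals are exact, so that cut-off is not part of the analysis.
- A reader might take it as established that the wrong test was run. The software settings are not given, so only the numerical agreement can be asserted.

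**Conclusion.** The point holds as a minor correction. The Table 6 powers agree with a score test at the asymptotic cut-off and not with the exact method that the footnote cites and the analysis will use. They exceed the exact powers by 0.3 to 2.0 points per row, and the stated floor of 87% is 85.5% under the planned analysis.

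This rests on 240 and 60 evaluable subjects, one-sided 0.025, the rounded true rates printed in Table 6, and reading the exact method as the unconditional score test described in Section 4.7.3.1. The source of the printed values is inferred. The primary endpoint is untouched.

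**What to change.** Replace the power column of Table 6 with the exact values, in table order:

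- runny nose 93.0, 6.5, 88.2
- sore throat 90.0, 11.5, 89.9
- cough 98.7, 80.0, 91.9
- headache 85.5
- muscle aches 91.8
- chills 93.9
- tired/weak 97.0, 84.3, 88.6

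In the synopsis and in Section 4.7.2, change the floor from 87% to at least 85% (rounded down, since it is a minimum) and keep the zero-difference condition.

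If the sponsor prefers to keep the table, footnote a should be reworded after checking the software settings. If they confirm the inference, it should say that the powers are for a score test with an asymptotic cut-off, which differs from the planned exact intervals. The floor still needs restating in both places.

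The cost is one table column or footnote and two sentences. The design, sample size and analysis do not change.
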